TESTING AND INTERVENTION. Participants will attend a baseline visit at the Center for Advanced Human Brain Imaging Research (CAHBIR) at Rutgers University, during which functional magnetic resonance imaging (fMRI) coupled with a meal test will be performed to assess peripheral and central feeding pathways (7, 8). fMRI scans will be performed during resting state to assess functional connectivity of feeding related networks, with a specific focus on connectivity between the hypothalamus, insula, anterior cingulate, ventromedial/orbitofrontal prefrontal cortex and amygdala (9, 10). Activation to food (vs non-food) images will be assessed to index responsivity to appetitive feeding networks including the above regions and the ventral striatum using paradigms that have previously been found to be sensitive to trait and state in multiple studies (11-13). Thereafter participants will consume a liquid meal (525 kcal; Ensure Plus, Abbott). fMRI will be repeated immediately after the meal. Participants will attend a second visit at the IFNH, during which laboratory work coupled with a meal test will be performed to assess satiety hormones and inflammatory markers. Fasting blood draw will be taken, and the participants will consume a liquid meal (525 kcal; Ensure Plus, Abbot) followed by blood draws at 30, 60, 120, 180 and 240 min postmeal. Upon completion of baseline testing and providing a fecal sample, participants will consume NBT-NM108 (a mixture of inulin, Fibersol-2, and brans of oat, wheat, corn and sorghum; Notitia Biotechnologies) daily for 4 weeks. At the completion of the 4-week intervention, all sampling and testing will be repeated as per baseline. At baseline and end of intervention, participants will be interviewed with appetite and physical activity questionnaires (Appendix C and G) and requested to complete a 24-h food recall using MyFitnessPal, a mobile health app on their phone.

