## B. Data Points

- Gut microbiota composition: fecal samples will be collected at weeks 0 and 4.
- fMRI scans will be completed at baseline and end of intervention.
- Blood parameters (satiety hormones and inflammatory markers) at minutes 0, 30, 60, 120, 180, and 240 post-meal at week 0 and week 4.
- Appetite and physical activity questionnaires at weeks 0 and 4.
- Calorie count calculated via 24-h food recall on MyFitnessPal at weeks 0 and 4.

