## D. Endpoints

[figure not shown]
- 1. Primary Outcome
  - Gut microbiota composition at Weeks 0 and 4
- 2. Secondary outcomes:

- Weeks 0, 1, 2, 3, and 4
  - a. Weight measured in pounds
- Weeks 0 and 4
  - a. Hormones related to satiety and hunger include ghrelin, peptide YY (PYY), leptin, glp-1/GIP, insulin, glucose
  - b. Inflammatory markers include c-reactive protein (CRP), interleukin 6 (IL-6) and tumor necrosis factor-alpha (TNF-), adiponectin
  - c. Outcome of fMRI showing responsivity of appetite feeding networks in the brain
  - d. Caloric intake recorded in MyFitnessPal application
  - e. Appetite behavior measured by hyperphagia questionnaire and visual analog scale (VAS)
  - f. Physical activity measured by physical activity questionnaire

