## 1.5 Sample Size Justification

No power calculation is performed for this pilot study. We aim to recruit 10 patients with hyperphagia(5 male and 5 female) to capture a reasonable degree of variations in gut microbiota composition.

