## 4.3 Number of Subjects

A. Total Number of Subjects

10 patients; 5 male and 5 female

- B. Total Number of Subjects If Multicenter Study N/A
- C. Feasibility

DEEP6 identified 26 patients via EPIC system who had the diagnosis of PWS with only 5 patients meeting our inclusion criteria. For this reason we are expanding our diagnosis coding to include hyperphagia syndrome. Given hyperphagia is a hallmark feature of PWS and the particular behavior we are aiming to study, this expansion should improve our subject pool and allow us to enroll 10 patients.

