## 6.0 Data Management Plan

## 6.1 Data Analysis

Microbiome sequencing data will be analyzed based on the amplicon sequence variants (ASVs) [28] to determine the gut microbiota composition using QIIME 2 [29]. Shannon index and ASV richness will be used to assess alpha diversity. Principal coordinate analysis will be used to compare and visualize dissimilarity in gut microbiota structure between samples based on beta diversity (Weighted and Unweighted UniFrac distance) and statistical differences will be tested using permutational multivariate analysis of variance (PERMANOVA). PICRUSt 2 will be used to predict the functions of individual ASVs and the collective functions of the gut microbiota at the gene content and pathway levels [30]. Global functional profiles of the gut microbiota will be compared and visualized by principal component analysis. Repeat measures correlation will be used to assess the relationships between ASVs [31], followed by ASV clustering based on co-abundance patterns. Multivariate methods such as MaAsLin2, that allow adjustment for confounding variables and model the covariates as random effects, will be applied to interpret the relationship between ASVs / ASV co-abundance groups / functions and the clinical metadata.

Difference in continuous variables of metadata, such as measurements of hormones, blood inflammatory markers and total caloric intake, between week 0 and week 4 will be tested by Paired t-test (two-tailed) if meeting normal distribution or Paired Wilcoxon Signed-Rank test (two-tailed) if not meeting normal distribution. Difference in the continuous variables of metadata between male and female will be tested by Student's t-test (two-tailed) if meeting normal distribution or Mann-Whitney test if not meeting normal distribution. Fisher's exact test will be used to compare proportions of categorical metadata, such as data in the appetite and physical activity questionnaires, between male and female, and between Week 0 and Week 4. The false discovery rate will be applied for multiple testing, where appropriate.

HRP-503a - TEMPLATE - Interventional Research Protocol 1.1.21 Protocol Title: Gut microbiota and hyperphagia in PWS Protocol Version Date: October 7, 2022

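### Section 6.1 tests categorical questionnaire data at Week 0 versus Week 4 with Fisher's exact test, which treats 10 paired answers as two independent groups

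*Combined protocol and SAP*

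**What the plan says.** Section 6.1 (Data Analysis) gives one rule for categorical data: "Fisher's exact test will be used to compare proportions of categorical metadata, such as data in the appetite and physical activity questionnaires". The sentence goes on to name two comparisons, "between male and female, and between Week 0 and Week 4".

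The design has a single arm. Section 4.3 sets the number at "10 patients; 5 male and 5 female", and section 1.3 B (Data Points) lists "Appetite and physical activity questionnaires at weeks 0 and 4". Section 1.3 A confirms that participants are interviewed with both instruments at baseline and again after the intervention. Section 1.3 D makes appetite behaviour (item e) and physical activity (item f) secondary outcomes.

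For continuous variables over the same interval, the same paragraph of 6.1 plans a paired analysis: the difference "will be tested by Paired t-test (two-tailed) if meeting normal distribution or Paired Wilcoxon Signed-Rank test (two-tailed"), the choice depending on normality. For continuous variables by sex it plans unpaired tests. No paired test for categorical data appears anywhere in the supplied text.

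**The concern.** Fisher's exact test takes its p-value from a reference distribution for two independent samples. Male versus female meets that condition. Week 0 versus Week 4 does not, because every Week 4 answer comes from a person who also answered at Week 0. The test would treat 10 pairs as 20 unrelated answers and discard the information on who improved and who worsened.

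The plan separates paired from unpaired comparisons for continuous data, then uses one unpaired test for both comparisons when the data are categorical. That is a rule that does not fit the design, not a missing detail.

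At stake is how the categorical questionnaire results are read. With 10 pairs, the same data can fall on one side of a significance threshold with Fisher and on the other with a paired test.

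**Working it through.** The plan states no power, significance level or calculated sample size, so there is no figure of its own to reproduce. The check compares the planned test with a paired one on the same data.

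**Inputs.** n = 10 participants (sections 1.5 and 4.3), each measured at Weeks 0 and 4 (sections 1.3 A and B). Assumed, because the documents do not give them: a yes/no item, two-sided 0.05, the prevalences and the within-person correlations.

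**Notation.** Of the 10 pairs, a answer yes at both weeks, b change from yes to no, c change from no to yes, and d answer no at both. Fisher sees only the margins, a + b at Week 0 and a + c at Week 4. Exact McNemar sees only b and c: its p-value is the two-sided binomial probability of a split at least as uneven as b against c, out of b + c, with probability 1/2.

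**Same margins, different pairing: 8/10 falls to 2/10.** Fisher, for every pairing: 2 × (1 + 100 + 2025) / 184756 = 4252 / 184756 = 0.023. Exact McNemar:

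| Changers (b against c) | Calculation | p |
|---|---|---|
| 6 against 0 | 2 / 64 | 0.031 |
| 7 against 1 | 2 × (1 + 8) / 256 | 0.070 |
| 8 against 2 | 2 × (1 + 10 + 45) / 1024 | 0.109 |

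Other margins behave alike. For 7/10 to 1/10, or 9/10 to 3/10, Fisher gives 0.020 and McNemar 0.031 or 0.070. For 5/10 to 0/10, Fisher gives 2 × 252 / 15504 = 0.033 and McNemar 2 / 32 = 0.0625; 10/10 to 5/10 gives the same pair of values.

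**All possible tables.** There are 286 sets (a, b, c, d) that sum to 10. Fisher has p ≤ 0.05 in 48 and McNemar in 36. Both are significant in 36, Fisher alone in 12, McNemar alone in 0, neither in 238.

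**Rejection rates.** These are exact multinomial sums over the 286 tables. The cell probabilities come from a bivariate normal variable cut at the assumed prevalences, with latent correlation 0 / 0.5 / 0.8. The last column is the chance that the two tests disagree.

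| Week 0 to Week 4 | Fisher, % | McNemar, % | Disagree, % |
|---|---|---|---|
| 50% to 50% (no change) | 1.28 / 0.28 / 0.03 | 0.90 / 0.21 / 0.02 | 0.38 / 0.07 / 0.01 |
| 20% to 20% (no change) | 0.76 / 0.18 / 0.02 | 0.17 / 0.03 / 0.003 | 0.58 / 0.14 / 0.02 |
| 80% to 20% | 64 / 64 / 65 | 56 / 62 / 63 | 7.3 / 2.5 / 1.3 |
| 50% to 10% | 30 / 26 / 25 | 19 / 18 / 17 | 10.3 / 8.8 / 8.1 |

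At 50% prevalence, latent correlations of 0.5 and 0.8 correspond to correlations of 0.33 and 0.59 between the yes/no answers themselves. If the answers correlate 0.5 directly, the no-change rates are 0.08% (Fisher) and 0.06% (McNemar).

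**The case against.** The strongest reply is that no practical harm is shown. Both tests address the same null hypothesis, equal proportions at the two weeks, so Fisher does not ask the wrong question. With zero or positive correlation its false-positive rate stays far below 5%, and its power is at least that of exact McNemar in every scenario above. It passes 5% only under strong negative correlation (about 6.8% at −0.8 with 50% prevalence), which is implausible for repeated questionnaires. The 12 of 286 tables are not equally likely, and the 0.109 example needs all 10 participants to switch their answer. Finally, item formats are in Appendices C and G, which were not supplied: a VAS or a summed score would on a plain reading follow the paired continuous rule, so the Fisher sentence may govern only some items.

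Most of this stands and limits the size of the point. The count of tables shows the direction of disagreement, not its frequency; the last column of the table gives the frequency under the stated assumptions. It does not rescue the rule. A test whose independence assumption the design breaks is not made valid by being conservative under favourable assumptions, and lower power for the valid test is no reason to keep the other. Any item that is categorical still falls under the sentence as written.

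**Conclusion.** The concern holds. Fisher's exact test is right for male versus female and wrong for Week 0 versus Week 4. The fault lies in its reference distribution, which assumes independent groups and makes the p-value blind to the pairing.

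The size is modest. At n = 10 and an assumed two-sided 0.05, every disagreement runs one way: Fisher significant, exact McNemar not. Under the assumed scenarios the tests disagree in at most 0.6% of trials with no true change, and in about 1% to 10% with a large one. Neither inflated type I error nor loss of power is claimed against Fisher.

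The affected outcomes are secondary, and how many of their items are categorical cannot be told from the supplied text. The primary outcome, microbiota composition, is not touched, and section 1.5 says "No power calculation is performed for this pilot study". The correction should be made because the rule is wrong as written and simple to put right.

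**What to change.** In section 6.1:

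1. Keep Fisher's exact test for male versus female only.
2. For categorical items at Week 0 versus Week 4, use the exact McNemar test for two categories or a marginal-homogeneity test for more than two. Report how many participants improved and how many worsened.
3. Optionally, as a clarification, state that any questionnaire item or scale with a numeric score, including the VAS, is analysed without dichotomising by the paired t-test or Wilcoxon signed-rank test already planned.

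The cost is wording only, with no new data, visits or participants. The downside is less favourable p-values and lower power. With 10 pairs, exact McNemar needs at least 6 changers all in one direction (p = 0.031) or, with one change the other way, 8 against 1 (2 × (1 + 9) / 512 = 0.039). In the assumed scenarios the power loss runs from about 1 point (80% to 20%, latent correlation 0.8) to about 10 points (50% to 10%, correlation 0). Dropout would leave fewer pairs and make this threshold harder to reach, which is a further reason to report the counts of changers and not the p-value alone.

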## **1.4 Preliminary Data**

Dietary fibers modulated gut microbiota and conferred clinical benefits in PWS patients. Children aged 3-16 years old (N=17 with PWS and N=12 with simple obesity) were prescribed a diet enriched with wholegrains, traditional Chinese medicinal foods and prebiotics (WTP diet) for 30-90 days (5). This diet was specifically formulated to include a large amount of dietary fibers with diverse physicochemical structures to maximize carbohydrate fermentation by the gut microbiota. The diet induced significant and yet

similar shifts in the overall gut microbiota structure in both groups, an effect associated with improvements in metabolic parameters including body weight and glucose homeostasis (Figure 1). Importantly, based on a hyperphagia questionnaire, we observed a modest but non-significant improvement in the overall food-related behavior in PWS patients (P=0.074).

Our network analysis identified guild-level structure in the gut microbiota (Figure 2). When supplemented with dietary fiber, gut bacteria exhibited co-abundance patterns and formed genome interaction groups (GIGs) or "guilds" (an ecological group in which members exploit an environmental resource in a similar way and show co-abundant behavior). Three guilds, which included strains of beneficial bacteria such as Bifidobacterium were negatively correlated with body weight and HbA1c, while 9 guilds which contained many opportunistic pathogens such as LPS producers were positively associated with disease parameters. Taken together, we showed that high-fiber diet was a feasible and effective way to modulate gut microbiota in PWS patients, which conferred clinical improvements and may also alleviate hyperphagia.

[figure not shown]

Figure 2. Network analysis of the bacterial genomes. Genomes of the same color were grouped in the same guild. Size of the nodes indicated the abundance of genomes. Red and blue lines denoted positive and negative correlations respectively.

[figure not shown]
Interestingly, transplantation of the pre- and post-intervention gut microbiota from the same patient to germfree mice induced opposite responses in the recipient mice. While these mice had no genetic defects and were maintained on a standard chow diet, receiving the pre-intervention PWS gut microbiota alone was sufficient to induce inflammation, excessive fat accumulation and liver steatosis whereas the post-

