## Study Instruments:

- See Appendix C for the appetite questionnaire
- See Appendix G for the physical activity questionnaire
- MyFitnessPal application will be used to calculate caloric intake from 24-h diet recall

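### Section 6.1 assigns the appetite and physical activity questionnaires to a Fisher comparison of proportions between visits, states no analysis of their scores, and does not say how the VAS is tested

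*Combined protocol and SAP*

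**What the plan says.** The endpoint list (section 1.3 D) includes, as a secondary outcome at Weeks 0 and 4, "Appetite behavior measured by hyperphagia questionnaire and visual analog scale (VAS"). Physical activity by questionnaire is a further secondary outcome, and caloric intake is listed separately.

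Section 6.1 gives two rules for these clinical data:

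- **Continuous variables.** "Difference in continuous variables of metadata, such as measurements of hormones, blood inflammatory markers and total caloric intake" between the two visits are tested by "Paired t-test (two-tailed) if meeting normal distribution", otherwise by the paired Wilcoxon signed-rank test. The list is open-ended. It names no questionnaire score and no VAS.
- **Categorical variables.** Fisher's "exact test will be used to compare proportions of categorical metadata, such as data in the appetite and physical activity questionnaires". The questionnaires are the named example. The rule covers comparisons "between male and female, and between Week 0 and Week 4".

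The visible text defines no questionnaire total, category or cut-off. The instruments are in appendices that are not part of the text available here ("See Appendix C for the appetite questionnaire"; Appendix G holds the physical activity questionnaire). Section 1.4 reports the sponsor's earlier study of the same kind of instrument as one overall result: "based on a hyperphagia questionnaire, we observed a modest but non-significant improvement in the overall food-related behavior in PWS patients (P=0.074"). Section 1.5 states that no power calculation was done.

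**The concern.** The stated objective (section 1.1 A) concerns microbiota, appetite control and feeding behaviour. The questionnaire is one of the two instruments that the endpoint list puts under appetite behaviour. A comparison of proportions counts who falls in which category and ignores how far each patient moved. With 10 patients there is little information to spare.

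The sentence has a second fault. Fisher's exact test compares independent groups, whereas Week 0 and Week 4 hold the same patients. The test is therefore not valid for that comparison, whatever the scale of the items.

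The two faults are separate. Replacing Fisher with a paired test on the same proportions corrects the second and leaves the first. At stake is whether this pilot gives a usable estimate of change in appetite behaviour. The plan as written produces neither a mean change nor an interval for it.

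**Working it through.** The plan states no power figure, so there is none to reproduce. What follows is an illustration.

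**From the documents:** 10 patients, single group, two visits (sections 1.5 and 4.3); two-tailed paired tests for continuous data and Fisher for categorical data (section 6.1).

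**Assumed:** alpha 0.05 (none is stated), normal scores, no dropout, no false discovery rate adjustment, correlation ρ between visits of 0.5 to 0.85, and a two-category split. The plan contains no such split; it stands in for categories that are not defined.

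**1. Score analysis.** For a mean change of dz SDs of change, the paired t-test has noncentrality dz × √n. With dz = 1.0 and n = 10 this is 3.16 on 9 df, giving power of 80%. The Wilcoxon test is about 1 to 3 points lower.

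**2. The same change, split at the baseline median.** A change of 1.0 SD of change equals a shift of √(2(1−ρ)) SDs of the score. The proportion above the baseline median falls from 50% to Φ(−shift). Power is by simulation:

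| ρ | Shift (score SD) | Above median at Week 4 | Paired t | Exact McNemar | Fisher |
|---|---|---|---|---|---|
| 0.5 | 1.00 | 16% | 80% | 10–11% | 15% |
| 0.7 | 0.77 | 22% | 80% | 5% | 6% |
| 0.85 | 0.55 | 29% | 80% | 1% | 2% |

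Placing the cut at the centre of the pooled distribution, which favours the categorical tests, gives McNemar 16%/6%/1% and Fisher 18%/7%/2%.

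**3. Why the categorical tests are weak at this size.** Exact McNemar with 5 v 0 changes gives p = 2 × (1/2)^5 = 0.0625; with 6 v 0, p = 2 × (1/2)^6 = 0.031. At least 6 of the 10 patients must therefore change category and, if exactly 6 do, all in the same direction. Fisher on 10 v 10 needs a contrast such as 10/10 v 5/10 or 9/10 v 3/10.

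**4. More categories and larger shifts.** ρ = 0.7, cuts centred on the pooled distribution:

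| Shift (score SD) | Paired t | Fisher, 2 categories | Fisher, 5 categories |
|---|---|---|---|
| 0.5 | 45% | 2% | 4% |
| 0.8 | 83% | 8% | 13% |
| 1.0 | 95% | 15–16% | 24% |
| 1.2 | 99% | 29% | 41% |
| 1.5 | about 100% | 50% | 68% |

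**5. Effect of ignoring the pairing.** With no true change, the two-category Fisher test rejects in 0.3% of runs or fewer (ρ 0.5 to 0.8), against a nominal 5%.

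**6. Limit of the score analysis itself.** At dz = 0.5 the paired t-test has only 29% power with n = 10. If the earlier P=0.074 in 17 patients came from a paired t-test (section 1.4 does not say), then t = 1.912 and dz = 1.912/√17 = 0.46. Power at n = 10 would be 26% for the score, against 0.7% (two categories) or 2.5% (five categories) for Fisher at ρ = 0.7.

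**The case against.** The strongest reply is that the plan cuts no score into categories. It limits Fisher to categorical data, which may mean item-level answers, and any total or VAS could fall under the open-ended continuous rule. The appendices are not visible, so it is unknown whether items are nominal, ordinal or summed. Section 1.4 gives neither the scoring nor the test behind the earlier result. The study is also a pilot that claims no power.

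Much of this stands, and it rules out several stronger readings that a reader might infer:

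- **That section 6.1 treats the VAS as categorical.** It does not mention the VAS. The plan is silent or ambiguous on it.
- **That almost all power is lost in every case.** The 1–2% figures belong to ρ = 0.85, where the shift is only 0.55 SD of the score. At shifts of 1.2 to 1.5 SD Fisher keeps about 30–70% (ρ = 0.7, cuts at the pooled centre).
- **That these are the only direct measures of feeding.** "Caloric intake recorded in MyFitnessPal application" is also an endpoint, and section 6.1 tests it as continuous.
- **That the main objective rests on Fisher's test.** Section 6.1 studies the link between microbiota and clinical data by multivariate methods such as MaAsLin2. Fisher covers only the visit and sex comparisons.
- **That a null result would be read as no behavioural effect.** Nothing in the documents says so, and section 1.4 describes its own non-significant result with care.

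The reply does not remove the point. The questionnaires are the named example of categorical data, no score analysis is stated, and the Week 0 v Week 4 use of Fisher is explicit. Disclaiming power in a pilot is a reason to estimate the change, not a reason to compare proportions.

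**Conclusion.** The point holds in limited form. Section 6.1 assigns questionnaire data to a comparison of proportions between visits, states no score analysis, leaves the VAS unassigned, and uses an independent-groups test on the same patients.

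Under the assumed median split, an analysis with about 80% power on the score has 1–11% as an exact paired two-category test and 2–15% as Fisher. With five categories, or larger shifts, the gap narrows but remains. Pairing alone does not recover the loss, so most of the gain comes from keeping the score.

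The direction of the loss follows from the method. Its size depends on the assumed normality, split, correlation and effect, none of which the plan states, and on questionnaire items that can be summed to a score. The score analysis would not make the pilot well powered for a modest effect. It would give an interpretable estimate. The plan should be corrected, but the point does not undermine the primary outcome, which is microbiota composition.

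**What to change.** In section 6.1:

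1. Name the hyperphagia questionnaire score, the VAS and any summed physical activity score, and assign them to the existing paired t/Wilcoxon rule for Week 0 v Week 4, reported as mean change with 95% CI.
2. State how each score is formed, by reference to Appendices C and G.
3. Keep categorical tests only for items that are truly categorical. Between visits use a paired test for these, for example exact McNemar for two-category items. Fisher can stay for male v female.

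Choosing one appetite measure as the main behavioural result is optional and is not needed to correct this sentence.

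Cost: a change of wording and minor analysis work. No new data, visits or patients.
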